5. Measurement of carotid intima media thickness using a General Electric LogiQ ultrasonographic device with border detection software. A 14.2 x 47 mm lineal GE 12L-RS transducer was used. International measurement norms were used ³.
6. Measurement of liver fat infiltration using the same ultrasonographic device but with a convex multifrequency (2 – 5.5 MHz) 4C RS GE transducer. Fatty infiltration was ascertained using Hamaguchi score ⁴. We have previously validated this technique against liver fat measurement using magnetic resonance spectroscopy.

Participant features were reassessed with the new laboratory determinations and those who continued to comply with inclusion criteria were randomized into two groups, balancing by gender, age, body mass index and urine albumin excretion expressed per mg of creatinine. Randomization was carried out using an iteration software based on random number generation. The output was an individual number for each patient. This number was sent to the oil manufacturer, who had the codes for each number and prepared the supplement to be used.

1. Active supplement contained 282 mg of docosahexanoic and eicosapentanoic acids per ml.
2. Placebo supplement: Contained corn oil

Participants were instructed to drink 13 ml of the supplement per day in one or two doses. Both supplements had a lemon flavor and were indistinguishable due to deodorization technology used

to prepare them. Therefore the investigators and the participants were blinded to the treatment allocation.

The intervention period lasted 3 months. Participants were cited every two weeks to provide them with a new bottle of supplement. They returned the used bottle and the residual content was measured to determine compliance. They were also interrogated about adverse events or other eventualities.

At the sixth week and at the end of the intervention at 12 weeks, participants were subjected to the same assessments done at baseline.

All participants could call the investigators in any moment if they an intercurrent problem. If a subject failed to attend an appointment, he or she was called by phone or visited at their houses to find out the reason for not showing. If a subject declined to continue in the study, he or she was considered as a loss from follow up.

Data analysis:

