Until the end of the intervention period for all participants, they were only identified with their allocation number. Once the intervention ended, each participant was classified as pertaining to group 1 or 2, without knowing which was the group receiving the active supplement. All red cell membrane fatty acid composition measurements, was analyzed when all statistical analysis of the rest of the variables were done, to maintain the blinding. An intention to treat analysis was performed.

Normality of variable distribution was analyzed using Shapiro Wilk test. Since most variables had a non-normal distribution, results are expressed as median (interquartile range). By the same token, non-parametric statistical methods were used to compare variables. Chi square or fisher tests were used to compare proportions. Differences between groups were compared using Kruskal

Wallis test. To assess changes in repeated measures of a single parameter a mixed linear regression model for repeated measures was used⁵. Significance level was set at 0.05

The main outcome of the study was set as a reduction in urine albumin excretion by 20% or more. We anticipated that 35% more participants receiving the active product than those receiving placebo would attain this reduction. Thus, the sample size to obtain results with an α of 0.05 and a power of 0.8 was 38 participants per group.

Results:

Participant flow is shown in figure 1. We randomized 50 participants per group and lost five in corn oil group and four in Ω -3 group. The demographic features, body mass index and baseline albumin excretion of participants randomized to each group are shown in table 1. No differences between groups were observed, therefore the premises of randomization were correctly attained. Red blood cell membrane phospholipids fatty acid composition during the study are shown in table 2. Patients receiving the active supplement had significant increases in eicosapentanoic and docosahexanoic fatty acid levels.

A 20% reduction in urine albumin excretion was attained in 13 participants of group 1 and 19 participants of group 2 (fisher $p= 0.274$). The clinical and laboratory parameters in the three assessment periods for groups 1 and 2 are observed in table 3.

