Summarizing, participants receiving corn oil maintained their pulse wave velocity during the follow up while controls experienced an increase in this parameter. Triacylglycerol levels decreased significantly in the Ω -3 group and glycosylated hemoglobin increased significantly in both groups

The compliance with the study product for groups 1 and 2, calculated measuring the leftovers was 88.7 (74-97) and 89.6 (77-98) %, respectively ($p= 0.99$). Eighty nine adverse events were recorded (48 in group 1 and 27 in group 2, $p = \text{NS}$). Of these, two were severe (a severe hyperkalemia and

the discovery of a cervical mass that resulted in a medullary thyroid carcinoma, both in participants of group 1). Mild gastrointestinal symptoms were reported by 12 and 14 participants in groups 1 and 2 respectively.

Preliminary conclusions:

1. The primary outcome measure of the study was not attained, since urine albumin excretion decreased by 20% or more in a similar proportion of participants in each intervention group.
2. The striking reduction in serum triacylglycerol observed in participants receiving Ω -3 fatty acids is a known pharmacological effect of Ω -3 fatty acids.
3. The deterioration of glycosylated hemoglobin in both groups, may be associated with the fact that participants received 110 Kcal/day of extra calories with the supplement.
4. The lack of increase in pulse wave velocity in group 2 may indicate that the supplement that this group received had a favorable effect on arterial stiffness.
5. The supplement was well tolerated. The lack of differences between groups in compliance and gastrointestinal complains indicates that the fish oil effectively almost completely deodorized.

[figure not shown]
Figure 1

Table 1: Initial features of randomized participants expressed as median (interquartile range)

	Gender (F/M)	Age (years)	Body mass index (kg/m²)	Urine albumin (mg/g creatinine)
Corn oil				
Group	26/24	66 (58-74)	31 (27.2-35.3)	604.5 (212-1234)
Ω-3 group	23/27	67 (56-74)	33.5 (30-37.3)	365.5 (157-1079)
Difference		NS	NS	NS

Table 2: Changes in red blood cell membrane phospholipids fatty acid composition. Values expressed as median (interquartile range) in mg/100 mg of total fatty acids

	Corn oil group (n=45)			Ω-3 Group (n=46)			p ¹
	Basal	Six weeks	Final	Basal	Six weeks	Final	
Pentadecanoic Acid (C15:0)	0.2 (0-3)	2.3 (0-3.2)	2 (0-3)	0.2 (0-2.9)	1.2 (0-3.2)	2.3 (0-3.3)	b

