Hdl cholesterol (mg/dl)	43.1 (37.1-52.3)	44.2 (36-51.6)	41.7 (35.3-53.2)	41.3 (35.2-54.4)	42.7 (35.6-53.8)	41.55 (37.8-51.8)	
Triacylglycerol (mg/dl)	147 (117-219)	133 (96-220)	150 (106-219)	163.5 (111-238)	125.5 (90-173)	117.5 (90-167)	c
Serum creatinine (mg/dl)	1 (0.82-1.76)	1.09 (0.79-1.78)	1.08 (0.81-2.06)	1.01 (0.79-1.33)	0.98 (0.75-1.57)	1.04 (0.8-1.37)	
Urine albumin excretion (mg/L)	370.6 (140.9-756.2)	344.3 (132.1-1096.5)	513.9 (185.4-978.7)	375.35 (146.5-584.4)	360.85 (162.9-1099.6)	467.9 (144.6-1005.2)	
Blood urea nitrogen (mg/dl)	22.3 (16.7-36.7)	20.5 (16.3-37.5)	20.7 (16.1-36.9)	18.95 (15-25.5)	19.6 (15.4-28.6)	19.15 (13.6-28)	
Urine creatinine excretion (mg/dl)	78 (56-100)	95 (69.5-113.5)	80 (57-118)	91.5 (62-135)	99.5 (62-126)	90.5 (68-121)	
Glycosylated hemoglobin (%)	5.9 (5.4-6.7)	6.2 (5.4-6.8)	6.2 (5.6-6.9)	6.35 (5.7-7.2)	6.45 (5.8-7.2)	6.5 (5.9-7.4)	b
Urine albumin/creatinine ratio (mg/g)	541 (173-1125)	561.5 (129-1063)	678 (149-1217)	363 (157-1030)	435 (164-950)	492 (129-1071)	

Table 3 continuation

	Corn oil group (n=45)			Ω-3 Group (n=46)			p [¶]
	Basal	Six weeks	Final	Basal	Six weeks	Final	
Urine urea nitrogen (mg/dl)	569.6 (439.3-784.2)	570.5 (467.95-783.4)	615.6 (433.6-803.3)	629.45 (526.6-824.9)	659.4 (444.6-881.3)	594.1 (488.3-763.6)	
C Reactive protein (mg/L)	1.68 (1.11-4.11)	1.81 (0.99-4.49)	1.91 (0.99-5.22)	3.265 (1.54-5.27)	2.5 (1.31-5.35)	2.14 (1.15-5.85)	
β2 microglobulin (mg/L)	2.7 (1.9-5.1)	2.7 (2-5)	2.4 (2-5.1)	2.35 (1.8-3.4)	2.3 (1.8-3.8)	2.2 (1.7-3)	
Interleukin-6 (pg/ml)	0.3 (0.2-0.4)	0.3 (0.2-0.3)	0.2 (0.2-0.4)	0.3 (0.2-0.4)	0.3 (0.2-0.4)	0.3 (0.2-0.4)	
Cistatin-C (mg/L)	1 (1-1.9)	1.1 (1-2.1)	1.2 (1-1.8)	1.1 (0.9-1.6)	1.2 (1-1.8)	1.2 (0.9-1.6)	
Estimated glomerular filtration rate (ml/min/1.73 m ²)	68 (31.2-80)	67 (28.6-75.9)	60.1 (34.6-76.5)	60.7 (42.4-81.9)	58.5 (33.7-73.9)	60.6 (39.6-78.9)	

[¶] = significance for differences between groups determined by a mixed effects lineal regression model for repeated measures. ^a = difference between groups without intervention effect, ^b= intervention effects without differences between groups ^c= intervention effect with differences between groups (Ω-3 fatty acid effect

References:

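### The pulse wave velocity summary sets the placebo arm against the controls and most likely names the wrong arm; the lack of increase claimed in conclusion 4 has no printed estimate behind it

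*Combined protocol and SAP*

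**What the plan says.** Material and methods identifies the control product: "Placebo supplement: Contained corn oil". Data analysis explains that after the intervention each participant was "classified as pertaining to group 1 or 2, without knowing which was the group receiving the active supplement". No later sentence unmasks those two numbers.

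The PWV result then appears in three places:

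- **Results, summary sentence:** "participants receiving corn oil maintained their pulse wave velocity during the follow up while controls experienced an increase in this parameter".
- **Preliminary conclusions, item 4:** "The lack of increase in pulse wave velocity in group 2 may indicate that the supplement that this group received had a favorable effect". The sentence goes on to name arterial stiffness as what was favourably affected.
- **Table 3:** the PWV row carries code c, defined in the footnote as "intervention effect with differences between groups" and bracketed there as an omega-3 effect. Augmentation pressure and augmentation index carry code b, "intervention effects without differences between groups". Reflection magnitude carries no code.

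Two statements in Results bear on the group key. One links the numbered groups to the table: "The clinical and laboratory parameters in the three assessment periods for groups 1 and 2 are observed in table 3". The other gives the primary outcome, "attained in 13 participants of group 1 and 19 participants of group 2", with a Fisher p-value of 0.274.

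**The concern.** In a two-arm trial with a corn oil placebo, the corn oil arm is the control arm. A sentence in which corn oil held steady while controls rose cannot be right as written, whichever number each group carries. A reader who quotes it alone would credit the placebo.

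Item 4 does not repair this, because it names a group number and not an oil. A reader who turns to Table 3 for the answer finds PWV medians that rise in both arms and a letter in place of a result.

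The primary outcome was not met, and the conclusions describe the triacylglycerol reduction as a known effect. PWV is therefore the only new favourable efficacy signal among the conclusions, and it should be possible to read from the text which oil it favours and by how much.

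**Working it through.** **Step 1. The sentence against the supplement list.** Material and methods makes corn oil the placebo. The summary sentence contrasts corn oil with controls. This contradiction needs no group key and no arithmetic.

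**Step 2. Recovering the group key.** Inputs, all from Results: 13 responders in group 1, 19 in group 2, Fisher p = 0.274; 50 randomized per arm, with five lost on corn oil (50 − 5 = 45) and four on omega-3 (50 − 4 = 46). The two-sided Fisher exact p-value sums the hypergeometric probabilities of all tables no more likely than the one observed.

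| Assumed key | Group 1 | Group 2 | Two-sided p |
|---|---|---|---|
| Group 1 corn oil, group 2 omega-3 | 13/45 (28.9%) | 19/46 (41.3%) | 0.2737 |
| Group 1 omega-3, group 2 corn oil | 13/46 (28.3%) | 19/45 (42.2%) | 0.1918 |
| All randomized (no key needed) | 13/50 (26%) | 19/50 (38%) | 0.2837 |

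Only the first row reproduces the printed figure. The match discriminates only among the reported arm sizes: 13/46 v 19/46, for example, also gives 0.2737. It is good evidence for the key, not proof.

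Three other points agree with it. Results sends the reader to Table 3 for groups 1 and 2, and the columns there run corn oil, then omega-3. The footnote brackets code c as an omega-3 effect. The other row of Table 3 with code c, triacylglycerol, is described in Results as a decrease in the omega-3 group.

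**Step 3. The two statements under that key.** Item 4 then says that PWV did not rise on omega-3. The summary sentence says that it did not rise on corn oil. They conflict, and the summary sentence is the one that also conflicts with the supplement list and with code c.

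**Step 4. What Table 3 shows for PWV (medians, m/s).**

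| Arm | Basal | Six weeks | Final | Final − basal |
|---|---|---|---|---|
| Corn oil | 9.3 | 9.7 | 9.7 | 9.7 − 9.3 = +0.40 (0.40/9.3 = 4.3%) |
| Omega-3 | 9.75 | 10 | 10.1 | 10.1 − 9.75 = +0.35 (0.35/9.75 = 3.6%) |

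The gap in median shift, omega-3 minus corn oil, is 0.35 − 0.40 = −0.05 m/s at the end. At six weeks it is (10 − 9.75) − (9.7 − 9.3) = 0.25 − 0.40 = −0.15 m/s. The interquartile ranges in the row are between 10.7 − 8.5 = 2.2 and 10.8 − 7.6 = 3.2 m/s wide. Both arms' medians rise, by nearly the same amount.

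**Step 5. Scope.** Of the four rows under the arterial stiffness heading, one (PWV) is coded as differing between groups, two are coded as changing without a group difference, and one is uncoded.

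**The case against.** The strongest reply is that the document as a whole leaves little doubt about what was meant. Item 4 says in words that group 2 did not increase and calls this favourable. The Fisher p-value, the column order and code c all make group 2 omega-3. On this view the summary sentence contains a slip of one arm name and the finding itself is intact. Most of this stands. A reader might infer from the faulty sentence that the direction of the PWV result is wide open, or that the trial found a benefit of placebo. The documents do not support either: the two possible one-word corrections are not equally plausible. Nor does the supplement list, which puts the active product first, count for much against the key. It numbers products, whereas the groups were numbered later and blind.

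A second reply is that rising medians prove nothing. The analysis was a repeated-measures mixed model, and a difference between marginal medians is not a within-patient change. This also stands. A reader might infer that Table 3 refutes the PWV effect; it does not. Code c asserts an effect judged at the 0.05 level. But the reply confirms that the claim rests entirely on a model result that is not printed.

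A third reply is that item 4 is hedged, sits under preliminary conclusions, and uses a class name that Table 3 itself applies to PWV. The hedge covers the causal step. It does not cover the flat statement that there was no increase, or the move from one flagged row to arterial stiffness generally. This is a matter of wording, and the lack of a code on the other rows does not show that they were unaffected.

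**Conclusion.** The point holds as a reporting contradiction in a secondary result that should be fixed. The summary sentence is wrong as written, because it opposes the placebo arm to the controls. It most likely names the wrong arm and so contradicts item 4. That second step rests on the inferred key (group 1 corn oil, group 2 omega-3), which the document never states. If the key were the reverse, the sentence and item 4 would name the same arm, but the misuse of controls would remain and item 4 would credit corn oil while code c credits omega-3.

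Separately, the lack of increase cannot be seen in the printed data (+0.40 m/s on corn oil, +0.35 m/s on omega-3), and its only support is a letter code with no size, sign, interval or p-value. The documents neither confirm nor refute an omega-3 effect on PWV. A reader might extend the doubt to the trial's main finding, but the negative primary conclusion does not depend on PWV and is unaffected.

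**What to change.** 1. State which oil is group 1 and which is group 2.
2. Check the arm labels against the data, then correct the summary sentence so that it agrees with item 4.
3. Print the mixed-model between-group difference in PWV change at week 12, with its sign, 95% CI and p-value.
4. Keep item 4, naming the oil and worded for PWV only, if that contrast supports it. Otherwise restate it as no demonstrated difference.

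No new data are needed. The cost is a few text corrections and possibly a short re-run of the model, since Data analysis does not say how time was modelled or whether a week-12 contrast was estimated. The downside for the sponsor is that a favourable secondary claim may be narrowed or lost.

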Eicosapentanoic Acid (C 20:5 n-3)	0.4 (0-0.7)	0.4 (0-0.7)	0.5 (0.2-0.8)	1.3 (0.4-3)	2.8 (1.4-3.3)	2.6 (1.1-3.5)	c
Docosadienoico Acid (C22:2)	0 (0-0)	0 (0-0)	0 (0-0)	0 (0-0)	0 (0-0)	0 (0-0)	
Docosahexanoic Acid (C22:6 n-3)	1.9 (1.3-2.8)	1.8 (1.4-2.6)	1.6 (1-2.4)	2.7 (2-3.7)	2.9 (2.2-3.8)	2.8 (2.2-4.2)	c
Total polyunsaturated	27.5 (23.4-30.8)	26.6 (24.1-30.3)	26.6 (22.4-29.9)	27.6 (23.2-31.5)	27 (24.3-31.4)	26.1 (22.1-29.9)	b

^a = significance for differences between groups determined by a mixed effects lineal regression model for repeated measures. ^b = difference between groups without intervention effect, ^c= intervention effects without differences between groups ^c= intervention effect with differences between groups (Ω -3 fatty acid effect)

Table 3: Measured parameters in both treatment groups, expressed as median (interquartile range)

	Corn oil group (n=45)			Ω-3 Group (n=46)			p [†]
	Basal	Six weeks	Final	Basal	Six weeks	Final	
Clinical parameters							
Systolic blood pressure (mm Hg)	129 (121-142)	134 (123-140)	133 (123-150)	135.5 (126-153)	137 (122-150)	138.5 (128-149)	
Diastolic blood pressure (mm Hg)	81 (73-87)	80 (73-86)	83 (74-90)	81.5 (73-95)	80.5 (75-92)	84.5 (74-93)	
Weight (kg)	76.4 (69.7-91.5)	77.4 (71.7-90.5)	77.6 (70.1-93.3)	90.4 (79.1-101.2)	91.05 (77.5-100.5)	91.2 (77.6-101.9)	
Waist circumference (cm)	104 (97-113.2)	104 (97.6-114)	105 (96-113)	110.5 (103.5-122.4)	112 (104.2-120)	111.25 (104-120.6)	
Carotid intima media thickness:							
Left (mm)	0.66 (0.6-0.83)	0.67 (0.57-0.84)	0.71 (0.58-0.83)	0.71 (0.61-0.88)	0.735 (0.62-0.85)	0.695 (0.59-0.82)	
Right (mm)	0.62 (0.55-0.715)	0.62 (0.54-0.73)	0.645 (0.555-0.755)	0.68 (0.6-0.78)	0.7 (0.61-0.78)	0.71 (0.61-0.79)	
Arterial stiffness measures							
Augmentation pressure (mm Hg)	8 (5-12)	9 (5-15)	12 (5-19)	9 (5-16)	11 (6-20)	12 (4-18)	b
Augmentation index (%)	18 (9-29)	23 (11-35)	25 (14-39)	20 (8-31)	27 (12-38)	23 (9-34)	b
Reflection magnitude (%)	66 (61-73)	70 (59-75)	69 (57-75)	67 (61-73)	67 (63-73)	66 (61-74)	
Pulse wave velocity (m/s)	9.3 (8.5-10.7)	9.7 (8.3-11)	9.7 (8.3-11.2)	9.75 (8.1-10.6)	10 (7.6-10.8)	10.1 (8-10.9)	c
Liver ultrasound							
Liver steatosis score (units)	3 (2-4)	3 (2-4)	3 (3-4)	3 (2-4)	4 (2-4)	3 (3-4)	
Laboratory values							
Fasting glucose (mg/dl)	94 (86-115)	97 (89-120)	95 (86-132)	99 (83-118)	107.5 (90-143)	103.5 (90-137)	
Total cholesterol (mg/dl)	165 (138-203)	162 (135-195)	160.5 (134-195)	170 (140-204)	167.5 (141-203)	154.5 (127-176)	

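### The adverse-event counts do not add up (48 + 27 = 75, not 89), so the printed NS cannot be verified and the arm with more events is not settled.

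*Combined protocol and SAP*

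**What the plan says.** The Results section, after the compliance figures, reports: "Eighty nine adverse events were recorded (48 in group 1 and 27 in group 2", followed by p = NS. The next sentence says that two of these events were severe, both in group 1, so they are part of the total and not an addition to it. Mild gastrointestinal symptoms are given separately, as 12 and 14 participants in groups 1 and 2.

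The Data analysis section sets general rules: "Chi square or fisher tests were used to compare proportions", and the Kruskal-Wallis test is named for differences between groups. Neither is tied to adverse events, and no counting unit (events, or participants with an event) is defined. Material and methods says participants were asked about adverse events at visits every two weeks.

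On numbers of participants: "We randomized 50 participants per group and lost five in corn oil group", with four lost in the omega-3 group, which leaves 45 and 46. Item 5 of the Preliminary conclusions states that the supplement was well tolerated.

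**The concern.** A safety total that disagrees with its own split by group means that at least one printed figure is wrong or that some events belong to no group. This is the only overall adverse-event comparison in the document, so a reader has nothing else to check it against.

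The mismatch also reaches the inference. Without a p-value, a counting unit or a linked test, the reader has to judge NS from the counts, and the counts allow different answers. In addition, the result is reported by group number, not by arm, so the reader must also work out which group received the active oil before drawing any safety conclusion.

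**Working it through.** **Inputs.** Total 89, group 1 = 48, group 2 = 27 (Results, adverse events); 50 randomized per group, 45 and 46 remaining (Results, participant flow); significance level 0.05 (Data analysis), taken here as two-sided.

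**Step 1: the sum.** 48 + 27 = 75. 89 − 75 = 14. 14/89 = 15.7%. The stated total is not reproduced.

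**Step 2: what a single misprint would imply.** If the total is wrong, it should be 75, with a split of 48 vs 27. If the group 2 count is wrong, it is 89 − 48 = 41. If the group 1 count is wrong, it is 89 − 27 = 62.

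**Step 3: an illustrative event-count test.** If events are independent and follow-up per participant is equal, then given N events in all, the group 1 count is binomial with parameters N and t1/(t1 + t2), where t is the number of participants. Exact two-sided p-values:

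| Number taken as wrong | Split | Events per participant (50/50) | Rate ratio (50/50) | p (50/50) | p (45/46) |
|---|---|---|---|---|---|
| Total | 48 vs 27 | 0.96 vs 0.54 | 1.78 | 0.020 | 0.015 |
| Group 2 | 48 vs 41 | 0.96 vs 0.82 | 1.17 | 0.53 | 0.46 |
| Group 1 | 62 vs 27 | 1.24 vs 0.54 | 2.30 | 0.0003 | 0.0002 |

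On this simple test one of the three corrections agrees with NS and two do not. The 45/46 column is only a sensitivity check, because it places every event among completers.

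**Step 4: how much clustering would restore NS for 48 vs 27.** z = (48 − 27)/√75 = 2.425. Dividing by √φ, where φ is the variance inflation from repeat events, z falls to 1.96 when φ = (2.425/1.96)² = 1.53. The document gives no per-participant counts, so this shows what NS would require and does not estimate φ.

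**Step 5: reading the counts as participants.** 48/50 vs 27/50 gives Fisher p of about 0.000001, and 48 exceeds the 45 or 46 who remained in either group. 48/50 vs 41/50 gives Fisher p = 0.051 and uncorrected chi-square p = 0.025. A count of 62 is impossible with 50 per group. The choice of unit and test therefore matters too.

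**Step 6: which arm is group 1.** The evidence points in both directions.
- For group 1 = corn oil: the Results say "The clinical and laboratory parameters in the three assessment periods for groups 1 and 2 are observed in table 3", and that table lists "Corn oil group (n=45") first. The primary result, "A 20% reduction in urine albumin excretion was attained in 13 participants of group 1 and 19 participants of group 2", is printed with Fisher p = 0.274. With 13/45 vs 19/46 the p-value is 0.2737; with the denominators swapped (13/46 vs 19/45) it is 0.192.
- Against: the Results summary says it was the corn oil participants whose pulse wave velocity was maintained, while item 4 of the Preliminary conclusions credits the lack of increase to group 2. Taken together, these make group 2 the corn oil arm. More weakly, Material and methods lists the active supplement as item 1 and the placebo as item 2.

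**The case against.** The strongest reply is that this is a slip in one results sentence with little consequence. Much of that stands. The design and the primary outcome are untouched. The tolerability conclusion cites compliance (p = 0.99) and gastrointestinal complaints (12 vs 14 participants; Fisher p = 0.82 on 45/46), not the overall event count. NS is also a convention that the document uses in Table 1, and general tests are listed, so the absence of a numeric p-value would be minor by itself. What the reply does not remove is the failed sum and the missing counting unit.

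Three stronger readings are tempting, and the document supports none of them.

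- A reader might infer that NS is false because 48 vs 27 gives p = 0.020. That p-value assumes independent events. Participants were questioned every two weeks, so one person may contribute several events, and a per-participant analysis could be non-significant. A misprinted group 2 count would also agree with NS.
- A reader might infer that the excess lies in the placebo arm and is therefore reassuring. The Fisher match and the Table 3 order do favour group 1 as corn oil, and the pulse wave velocity sentence that points the other way is itself confused, since it contrasts corn oil with controls. But the conflict is unresolved and no sentence states the mapping. The opposite inference, that the excess is in the active arm, is no better supported.
- A reader might note that the 14 missing events equal the 14 group 2 participants with gastrointestinal symptoms (27 + 14 = 41; 48 + 41 = 89). This is conjecture: the 14 are participants, not events, and nothing says they were left out of the 27.

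**Conclusion.** Wrong as written. The three adverse-event figures cannot all be right as a total and its complete split: 14 of 89 events (16%) are unaccounted for. This rests on addition alone.

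That NS cannot be verified follows from the missing counting unit and from the spread of illustrative p-values (0.53, 0.020 or 0.0003 with 50/50) according to which number is corrected. Those values assume independent events and equal follow-up, and they do not show that the groups differ. Which arm had more events is not settled, so no reassurance or alarm about the active oil should be drawn from this comparison. The same holds for attributing the two severe events, both in group 1, to an arm.

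The effect is limited. The primary outcome, gastrointestinal symptoms and compliance stand as reported. Only the general statement that the supplement was well tolerated needs confirming.

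**What to change.** 1. Reconcile 89, 48 and 27 with the adverse-event listing, and account for any event not assigned to a group.
2. State which arm is group 1 and which is group 2, and correct whichever pulse wave velocity statement is inconsistent with that.
3. Report by named arm (corn oil, omega-3) both the number of events and the number of participants with at least one event, out of the 50 randomized. This fits the stated approach: "An intention to treat analysis was performed".
4. Replace NS with a named test and a numeric p-value: chi-square or Fisher for participants, or for events a per-participant count comparison that allows for repeats (Kruskal-Wallis on counts per participant would fit the existing plan).
5. Then confirm or revise the general tolerability statement.

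The cost is a recount and one short reanalysis of data already held.

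### Conclusion 1 reads a non-significant Fisher test in completers as a similar response; the data give +12.4 points, 95% CI -7.1 to +30.6

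*Combined protocol and SAP*

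**What the plan says.** The Data analysis section defines the endpoint: "The main outcome of the study was set as a reduction in urine albumin excretion by 20% or more". On the planned effect it says: "We anticipated that 35% more participants receiving the active product than those receiving placebo would attain this reduction". From this it derives 38 participants per group at a significance level of 0.05 and power 0.8. The same section states: "An intention to treat analysis was performed".

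The Results section gives the flow: "We randomized 50 participants per group and lost five in corn oil group and four in" the omega-3 group. The primary result follows: "A 20% reduction in urine albumin excretion was attained in 13 participants of group 1 and 19 participants of group 2", with a Fisher p of 0.274. No denominators are printed beside these counts, and groups 1 and 2 are not named as arms. Tables 2 and 3 are headed with 45 corn oil and 46 omega-3 participants.

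Item 1 of the Preliminary conclusions then says the primary outcome was not attained, since "urine albumin excretion decreased by 20% or more in a similar proportion of participants in each intervention group".

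**The concern.** There are three linked faults.

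- **Inference.** A p-value above 0.05 does not show that two proportions are alike. That needs an interval that is narrow relative to a stated margin, and the readable text has neither for this outcome.
- **Label.** The reported p-value appears to come from completers, although the document declares an intention-to-treat analysis and 50 were randomised per arm.
- **Direction.** The result is reported by group number only. Item 4 of the conclusions credits group 2 with no rise in pulse wave velocity, while the Results summary says "participants receiving corn oil maintained their pulse wave velocity during the follow up while controls experienced an increase in this parameter". Read together, these make group 2 the corn oil arm, which would reverse the sign of the primary result.

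A reader could come away believing that equal response on omega-3 and corn oil had been demonstrated.

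**Working it through.** **Inputs.** Responders 13 (group 1) and 19 (group 2), from Results. Randomised 50 per arm, with 5 corn oil and 4 omega-3 losses, so 50 − 5 = 45 and 50 − 4 = 46, as in the Table 3 heading. Sidedness of the 0.05 level is not stated; two-sided is assumed.

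**1. Reproduce the stated p-value (two-sided Fisher exact).**

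| Reading | Group 1 | Group 2 | p |
|---|---|---|---|
| Completers, group 1 = corn oil | 13/45 | 19/46 | 0.2737 |
| All randomised, losses as non-responders | 13/50 | 19/50 | 0.2837 |
| Completers, group 1 = omega-3 | 13/46 | 19/45 | 0.1918 |

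Only the first gives the printed 0.274. A search over sizes from 38 to 50 also finds 43/45 and 46/46, but the document reports neither pair. The reported test is therefore a completer analysis, and the p-value points to group 1 being corn oil.

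**2. Difference and interval for completers.** 19/46 − 13/45 = 41.3% − 28.9% = +12.4 points. The Wilson 95% limits are 17.7% to 43.4% for 13/45 and 28.3% to 55.7% for 19/46. The Newcombe interval combines them:

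- lower: 12.4 − √[(41.3 − 28.3)² + (43.4 − 28.9)²] = 12.4 − 19.5 = −7.1
- upper: 12.4 + √[(55.7 − 41.3)² + (28.9 − 17.7)²] = 12.4 + 18.2 = +30.6

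The score interval is −7.3 to +30.9, so the choice of method does not matter.

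**3. All 50 per arm.** With losses as non-responders: 38.0% − 26.0% = +12.0 points, 95% CI −6.2 to +29.2, p = 0.284. Extreme assignments, as bounds only: if all five corn oil losses and no omega-3 losses responded, 19/50 − 18/50 = +2.0 points (p = 1.00). If all four omega-3 losses and no corn oil losses responded, 23/50 − 13/50 = +20.0 points (p = 0.060). These bounds assume group 1 is corn oil.

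**4. Opposite mapping.** Omega-3 13/46 (28.3%) minus corn oil 19/45 (42.2%) = −14.0 points, 95% CI −32.1 to +5.5. The loss bounds become 17/50 − 19/50 = −4 and 13/50 − 24/50 = −22 points.

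**5. What non-significance could have missed.** Against 13/45, a count of 23/46 gives p = 0.054. The first count to reach p < 0.05 is 24/46 (52.2%, +23.3 points, p = 0.033). With the control rate assumed to be the observed 28.9%, exact Fisher power at 45 and 46 is 14% for +10 points, 44% for +20, 63% for +25 and 91% for +35. A true 20-point difference would be missed about 56% of the time.

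**6. Reading the planned effect as absolute.** The control rate is not stated. For 30% versus 65%, n = {1.96√(2 × 0.475 × 0.525) + 0.842√(0.30 × 0.70 + 0.65 × 0.35)}² / 0.35² = 3.768 / 0.1225 = 30.8, so 31 per group, or 37 with continuity correction. Control rates of 25% to 40% give 36 to 37 with the correction, close to 38. A relative 35% increase from 30% would need 324 per group without the correction. The absolute reading is the plausible one, and the completer upper limit of 30.6 lies below 35.

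**The case against.** The strongest reply is that this is one loose word under a heading that calls the conclusions preliminary. No equivalence is claimed, the counts and exact p-value are printed, and the verdict of not attained is correct. The interval even excludes the planned 35 points. All of that stands, and it limits the consequence. It does not rescue *similar*, which is given as the reason for the headline conclusion.

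Table 3 also carries no significance marker for urine albumin in mg/L or mg/g. That is related evidence, but it concerns a continuous measure and is again only non-significance.

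On the analysis set, losses are disclosed by arm, the tables print 45 and 46, and the flow figure, which is not visible here, may give analysed numbers. The estimate hardly moves, so the fault is in the label.

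On the mapping, the case for group 1 as corn oil is better than the p-value alone. The Results point to Table 3 for groups 1 and 2, Table 3 lists corn oil first, and it marks pulse wave velocity as an omega-3 effect. The conflicting sentence sets corn oil against controls although corn oil is the placebo, so it may be a slip. It still needs correcting, because the direction of the primary result depends on the mapping.

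The 20-point benchmark in the power calculation is illustrative and is not in the document. The interval alone carries the argument.

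**Conclusion.** The concern holds. *Not attained* is right; *similar proportion* is unsupported. Completers show +12.4 points for omega-3 over corn oil (95% CI −7.1 to +30.6). This argues against the planned 35 points, read as absolute, but leaves open a smaller benefit or a disadvantage of about 7 points. The p-value of 0.274 belongs to a completer comparison under an intention-to-treat statement; counting all 50 per arm changes the estimate by only 0.4 points (12.4 − 12.0). The sign rests on group 1 being corn oil, which is inferred. Under the opposite mapping the estimate is −14.0 points (−32.1 to +5.5), and similarity is equally undemonstrated. The correction should be made, but it does not overturn the null result.

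**What to change.** - Report n/N, the risk difference and its two-sided 95% CI for completers, and label the p = 0.274 analysis as completers.
- Add the same figures for all 50 per arm with losses as non-responders, with the two extreme assignments as point bounds only.
- State which arm is group 1 and which is group 2, checked against the allocation code, and reconcile the pulse wave velocity sentence in the Results summary with item 4 of the conclusions.
- Beside the counts, name the albumin unit (Table 3 has both mg/L and mg/g) and the visit (week 6 or 12) that define response.
- Once the mapping is confirmed, reword item 1, for example: *The primary outcome was not attained: no statistically significant difference was shown in completers, and the estimate is imprecise (difference +12.4 points, 95% CI −7.1 to +30.6).*

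The cost is wording, arithmetic on counts already reported, and one look at the allocation code. No new data or model is needed.
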